**The second study vaccination will not be administered to a subject if any of the following criteria are met:**

- Meets the contraindication on the package insert to receipt of licensed influenza vaccine.
- As deemed necessary by the site principal investigator or appropriate sub-investigator for noncompliance or other reasons.
- Subject/parent(s)/legal guardian(s) refusal of further study vaccination.
- Withdrawal of consent.
- Subject is lost to follow-up.
- Termination of this trial.
- New information becomes available that makes further participation unsafe.

#### **5.3.4. Handling of Withdrawals and Discontinuation of Administration**

The primary reason for withdrawal from this trial will be recorded on the Study Status data collection form. Subjects will be encouraged to complete the Early Termination Visit. The Early Termination Visit procedures are listed in [Section 8](#).

Although subjects are free to withdraw at any time or may be withdrawn by the site principal investigator or appropriate sub-investigator at any time (see Section 5.3.3), those subjects who receive only one dose of study vaccine will be encouraged to remain in this trial for follow-up safety assessments (may be conducted by phone call/electronic communication (e.g., email, text message) rather than in person) continuing through approximately 3 months after their first study vaccination. These subjects will also be encouraged to provide a venous blood sample for immunogenicity and future-use research assays on all follow-up study visits. See the protocol-specific Manual of Procedures (MOP) for alternate follow-up requirements.

Every attempt will be made to follow all AEs, including solicited dose site and systemic reactions, unsolicited non-serious AEs, SAEs ongoing at the time of early withdrawal through resolution as per applicable collection times defined for the specific type of AE.

In the case of subjects who fail to appear for a follow-up safety assessment, extensive effort (i.e., three documented contact attempts via phone calls, emails, text messages, etc., made on separate occasions and followed by a certified letter) will be made to locate or recall them, or at least to determine their health status. These efforts will be documented in the subject's study records.

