#### **3.2. Study Outcome Measures**

##### **3.2.1. Primary:**

Safety:

- Frequency of solicited upper respiratory and systemic reactogenicity through approximately Day 8 after the first study vaccination.

- 
- Frequency of unsolicited non-serious adverse events from the time of study vaccination through 21 days after the first study vaccination.
  - Frequency of SAEs, regardless of seriousness or relationship to study vaccination, from receipt of the first vaccination throughout the entire study.
  - Frequency of New Onset Chronic Medical Conditions (NOCMC) and AESIs that develop from receipt of vaccination through 3 months after first study vaccination.

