#### **7.4.4. Visit 05, Day 92, Second Vaccination (Dose 2), Clinic Visit (Window: 91±14 days post first study vaccination)**

- Interim medical history, including an assessment for new medical conditions will be obtained by interview of parent(s)/legal guardian(s) and any changes since the previous clinic visit or contact will be noted.
- Criteria for administering QIV will be reviewed with parent(s)/legal guardian(s).
- Concomitant medications (limited to aspirin or salicylate containing products) will be recorded on the appropriate data collection form.
- All AESIs/NOCMCs/SAEs will be recorded on the appropriate data collection form. Reporting of AEs occurring since previous visit but before 2nd vaccination is limited to AESIs, NOCMCs, and SAEs.
- A targeted physical examination may be performed prior to the second study vaccination, if indicated based on review of interim medical history, by a study clinician licensed to make medical diagnoses and listed on the Form FDA 1572 as the site principal investigator or sub-investigator.
- Subject's/parent(s)/legal guardian(s) will be counseled on the avoidance of taking any aspirin or salicylate containing products for 30 days prior to receipt of the first vaccination through 21 days after the last vaccination.
- Oral temperature will be obtained to ensure eligibility. Subjects must not eat or drink anything hot or cold, or smoke within 10 minutes prior to taking oral temperature.
- A urine pregnancy test will be performed on all female adolescent subjects of childbearing potential and must be negative to ensure eligibility.
- A nasal swab for sIgA will be obtained.
- Approximately 6 mL of venous blood will be collected for serum HAI, HA/NA ELISA and neutralization assays.
- Approximately 16 mL of PBMCs will be collected for IFN- $\gamma$  ELISPOT and CFSE dilution/ICS assays. Note: PBMCs will not be collected if the HgB was consistently low through Day 57.
- Subjects will receive their second vaccination IM in whichever deltoid they prefer.

- Subjects will receive a single dose of study vaccine via IM injection into the deltoid muscle of the preferred arm. The site of injection and time of administration will be recorded on the appropriated data collection form. Subjects will be observed in the clinic for at least 30 minutes after the second study vaccination.

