#### **7.5. Final Study Visit, Visit 08, Day 366, Phone Call**

**(Window: 274±14 days post second vaccination)**

- Study personnel will contact parent(s)/legal guardian(s) by phone to solicit any SAEs, medical history information that have occurred since the previous clinic visit will be solicited. Based on the information, subjects may be asked to return to the clinic for evaluation.

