## 9. ASSESSMENT OF SAFETY

### 9.1 Specification of Safety Parameters

Safety will be assessed by the frequency and severity of:

1. SAEs occurring from the time of the first study vaccination through 12 months after the first vaccination.
2. AESIs (wheezing, otitis media) and NOCMCs occurring from the time of the first study vaccination through 3 months after the first vaccination.
3. Solicited Adverse Events – reactogenicity events occurring from the time of experimental (first) study vaccination through 7 days after the first study vaccination. See tables listed in [section 9.2.2 and 9.2.6](#) for local upper respiratory, respiratory tract assessment, and systemic symptoms:
4. Unsolicited Non-Serious Adverse Events –non-serious AEs occurring from the time of the first study vaccination through approximately 21 days after the first study vaccination.
5. Clinical safety laboratory AEs occurring at approximately 7 days after the first vaccination. Parameters to be evaluated include a WBC, HGB, Platelet Count, ALT, AST, Serum Creatinine, Ferritin level, PT and aPTT. HGB will also be repeated at Day 22 if there is a drop in HGB level from screen to Day 8 of  $\geq 0.5$  g/dL or results are  $<$  lower limits of normal. If unable to collect at Day 22, collect at Day 57. If drawn at Day 22 and the results are still low, repeat at Day 57. If HGB results are still low at Day 57, no further PBMC collection will be done. HGB and Ferritin level will be drawn at Day 113. If the ferritin is  $< 15$  ng/mL and/or the HGB is less than the lower limits of normal, will recommend follow-up with primary care provider for consideration of multivitamins with iron.

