### **9.3. Reporting Procedures**

Solicited upper respiratory assessment, respiratory tract assessment, and systemic reactogenicity events will be documented and reported from the time of experimental (first) study vaccination through 7 days after vaccination.

Unsolicited non-serious AEs will be documented and reported from the time of the first study vaccination through approximately 21 days after the first study vaccination.

SAEs will be documented and reported from the time of the first study vaccination through 12 months after the first vaccination.

AESIs (wheezing and otitis media) and NOCMCs will be documented and reported from the time of first study vaccination through approximately 3 months after first study vaccination.

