9.3.2. Unsolicited Adverse Events

When calculating the incidence of unsolicited AEs (i.e., on a per subject basis), each subject will only be counted once at the highest severity and/or relationship, and any repetitions of AEs within a subject will be ignored; the denominator will be the total number of subjects in the safety population. All AEs reported will be included in the summaries and analyses.

The number and percentage of subjects reporting at least one unsolicited AE will be summarized by MedDRA system organ class and preferred term. Denominators for percentages are the number of subjects who received the study vaccination summarized. A 95% CI will be presented for the percentage of subjects reporting any unsolicited AE (serious or non-serious) for each MedDRA system organ class and preferred term

A listing of all reported AEs by subject will be presented in [Listing 13](#), sorted by study group, subject ID, and AE Number.

The following summaries for unsolicited adverse events will be presented by MedDRA system organ class, preferred term, vaccination and study group:

- Subject incidence and total frequency of adverse events over time with 95% CI (Days 1-8, Days > 8) (Table 45);
- Summary of severity and relationship to study product (Table 46);
- Subject incidence and total frequency of related adverse events over time (Days 1-8, Days > 8) (Table 47);
- Subject listing of non-serious adverse events of moderate or greater severity (Table 49);
- Bar charts of the frequency and incidence of non-serious adverse events by severity and MedDRA system organ class (Figure 52 and Figure 53);
- Bar charts of non-serious adverse events by relationship (Figure 54 and Figure 55).

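### Protocol 5.3.4 asks one-dose subjects to stay for about 3 months, but the primary SAE outcome runs 12 months from dose 1 and the late SAE calls have no window for them

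*Protocol*

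**What the plan says.** The SAE outcome is primary. Protocol 3.2.1 sets its period as "from receipt of the first vaccination throughout the entire study". Protocol 9.1 lists as a safety parameter "SAEs occurring from the time of the first study vaccination through 12 months after the first vaccination", and Protocol 9.3 repeats the period for reporting: "SAEs will be documented and reported from the time of the first study vaccination through 12 months after the first vaccination". Protocol 9.4 gives the same 12 months. None of these makes an exception for subjects who miss dose 2.

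Protocol 5.3.4 addresses those subjects directly. They are encouraged to stay for safety assessments, by phone or electronic contact if need be, "continuing through approximately 3 months after their first study vaccination". The paragraph ends: "See the protocol-specific Manual of Procedures (MOP) for alternate follow-up requirements".

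Dose 2 (Visit 05) is due "91±14 days post first study vaccination". The two later SAE contacts are phone calls. In Appendix A they stand at Day 240 and Day 366 on the row for days after the first vaccination, with SAE assessment marked at both. Their windows are stated only from dose 2: 148±14 days for Visit 07 (Protocol 7.4.6) and "274±14 days post second vaccination" for Visit 08 (Protocol 7.5).

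One dose is enough to enter the Safety Analysis population (Protocol 11.4.1). For AE incidence, SAP 9.3.2 says "the denominator will be the total number of subjects in the safety population". SAP Table 38 gives the number and percentage of subjects with an SAE on that N, with no time at risk.

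**The concern.** The follow-up that 5.3.4 requests ends about 9 months before the outcome period does. Dose 2 falls due at days 77 to 105, so when a subject refuses it or has it withheld at Visit 05, the requested follow-up is nearly over and most of the SAE period lies ahead. No passage then gives that subject a windowed contact. After the follow-up period, reporting depends on the investigator happening to learn of an SAE and suspecting a link to study product (Protocol 9.2.3 and 9.3.1).

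The loss need not be random. Protocol 5.3.3 lists contraindication, investigator judgement, refusal and new safety information among the reasons for not giving dose 2, and some of these can be connected with what happened after dose 1. The halting rule on vaccine-related SAEs runs to each subject's last study visit (Protocol 9.5), so a shorter follow-up also shortens its reach. Safety is the primary objective here, with 25 children per arm.

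**Working it through.** **1. The plan's own safety-detection figure.** Table 3 (Protocol 11.2, SAP Appendix 1) gives the probability of seeing at least one event, 1 − (1 − p)^n. This treats every subject as observed for the whole risk period.

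| Event risk p | n = 25: computed / printed (%) | n = 50: computed / printed (%) |
|---|---|---|
| 10% | 92.8 / 93 | 99.5 / >99 |
| 1% | 22.2 / 22 | 39.5 / 40 |
| 0.1% | 2.5 / 3 | 4.9 / 5 |
| 0.01% | 0.25 / <1 | 0.50 / <1 |

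The table reproduces to within one point in every cell.

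**2. Two-dose subjects.** Dose 2 falls at 91 ± 14 = 77 to 105 days after dose 1, and Visit 08 at 274 ± 14 = 260 to 288 days after dose 2. Visit 08 therefore falls, in days after dose 1:

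- nominally at 91 + 274 = 365;
- at the earliest at 77 + 260 = 337;
- at the latest at 105 + 288 = 393.

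If both 29-day windows are used evenly (an assumption), there are 29 × 29 = 841 combinations. Of these, 29 fall on day 365, 406 before it (406/841 = 48%) and 406 after it.

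**3. One-dose subjects, if 5.3.4 is followed.** Take 3 months as 91 days. The observed fraction of the SAE period is 91/365 = 0.249, so 75% is unobserved.

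**4. Effect on the endpoint.** Let s be the share of one-dose subjects leaving at day 91. The documents do not give s, so it is varied. Two stand-ins exist, both about immunogenicity data: the 8% without data at Day 42 in a previous trial and the 10% dropout allowance (Protocol 11.2). With a constant hazard and 12-month risk p:

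- observed person-time fraction = 1 − s(1 − 91/365);
- crude SAE proportion on the full N = (1 − s)p + s[1 − (1 − p)^(91/365)];
- P(at least one event seen) = 1 − (1 − p)^(n(1 − s) + ns × 91/365).

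At p = 1% and s = 10%, the crude proportion is 0.9 × 1% + 0.1 × 0.25% = 0.925%, against 1%.

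| s | Crude proportion relative to the 12-month value | Relative under-count |
|---|---|---|
| 2% | 0.985 | 1.5% |
| 8% | 0.940 | 6.0% |
| 10% | 0.925 | 7.5% |
| 20% | 0.850 | 15% |

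Raising p to 10% changes these ratios by no more than 0.002.

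For 1, 3 or 5 such subjects among 50, observed time is 49.25, 47.75 or 46.25 of 50 person-years, a loss of 1.5%, 4.5% or 7.5%. At p = 1% and s = 10%, the detection probability falls from 22.2% to 20.7% for n = 25 and from 39.5% to 37.2% for n = 50.

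**The case against.** Several passages point to full SAE collection. Protocol 5.3.4 says encouraged, not required, and defers to a Manual of Procedures that is not among the documents; Protocol 6.3 makes the same referral. Protocol 7.6 and 7.7 keep SAE collection for the whole study at early termination and unscheduled visits. Protocol 9.3.3 follows pregnant subjects, who receive no further vaccination, for safety to the end of the trial. Appendix A marks SAE assessment at Day 240 and Day 366 without a one-dose exception. SAEs are listed individually by default, with percentages by arm and Fisher's exact test only if more than 5% of subjects report them (Protocol 11.4.2), which means at least 3 of 50. Some subjects miss dose 2 because they withdraw consent or are lost, and no rule can secure contact with them.

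All of this stands, and it rules out two stronger readings. A reader might infer that one-dose subjects have no scheduled SAE call at all; they do have nominal call days and lack only the window. A reader might also infer that these subjects are in fact followed for only 3 months, so that SAE frequency is under-counted. The documents show what 5.3.4 requests, not what the manual or the site does.

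The objection does not remove the conflict. The passages on whole-study collection schedule no contact for a one-dose subject, and an early termination visit happens once. Protocol 9.3.3 shows that the protocol can state full-length follow-up without further vaccination, yet 5.3.4 states about 3 months. Individual listing protects events that were recorded, not events that were never collected.

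**Conclusion.** The concern holds in a limited form. Protocol 5.3.4 conflicts with the SAE period in Protocol 3.2.1, 9.1, 9.3 and 9.4, and one-dose subjects have no window for the two late SAE calls. If 5.3.4 is followed, late SAEs in these subjects may be missed while the Table 38 denominator stays whole. The relative under-count is about 1.5% to 15% for an assumed one-dose share of 2% to 20% with a constant hazard. It would be smaller if SAEs cluster soon after dose 1, and larger if subjects who miss dose 2 carry a higher late risk.

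Two further inferences are not supported. Timing the final call from dose 2 does not in itself cause under-counting in two-dose subjects: the call falls nominally on day 365, and the range of 337 to 393 is symmetric, so early and late calls balance if the windows are used evenly. The 28-day maximum shortfall needs both visits at their earliest limit. Nor is it a material defect that Visit 05, the last scheduled AESI and NOCMC assessment, can fall on day 77. That period is itself only approximate (Protocol 9.3), and Visit 06 still takes an interim history that covers new medical conditions (Protocol 7.4.5).

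**What to change.** - **Protocol 5.3.4:** reconcile it with the 12-month SAE period, so that one-dose subjects who have not withdrawn consent are asked to stay in SAE follow-up, by phone, through 12 months after dose 1. Bring the Manual of Procedures into line.
- **Protocol 7.4.6, 7.5 and Appendix A:** for subjects without a second dose, give the Day 240 and Day 366 calls a window counted from dose 1. Leave the windows for two-dose subjects as they are.
- **SAP:** show the SAE percentages of Table 38 beside the number completing Day 366 by arm. Table 12 already produces that count, so no new data are needed.

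The cost is an amendment to the wording, up to two extra phone calls per one-dose subject, and a cross-reference or added row in one table.

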### **6.3. Modification of Study Intervention/Investigational Product for a Subject**

There will be no dose modifications. If a subject's second study vaccination is deferred, it should be rescheduled to occur within the acceptable protocol-specified window for that visit (Day 92±14 days post first study vaccination). If a protocol deviation occurs due to unforeseen circumstances related to the second vaccination window and the QIV cannot be given within the protocol window, the DMID Medical Officer must approve the second vaccination and the documentation of approval should be filed in the subject's chart.

Subjects who do not receive the second study vaccination will be encouraged to provide a venous blood sample for immunogenicity and future research testing. See Sections 5.3.3 and 5.3.4 for reasons for and handling of withdrawals and discontinuation of treatment. See the protocol-specific MOP for alternate follow-up requirements.

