#### **7.6. Early Termination Visit (if needed)**

The following activities will be performed at the early termination visit on subjects who withdraw, or are withdrawn or terminated from this trial:

- Interim medical history, including an assessment for new medical conditions will be obtained by interview of parent(s)/legal guardian(s) and any changes since the previous clinic visit or contact will be noted.
- Memory aid information will be reviewed with parent(s)/legal guardian(s) (if within 8 days after the last study vaccination).
- All concomitant medications (including solicitation for receipt of any non-study influenza vaccines) will be recorded on the appropriate data collection form (if within 21 days after the first study vaccination). If within 30 days of either vaccination through 21 days after the last vaccination, aspirin or salicylate containing products will be recorded.

- 
- Subject's/parent(s)/legal guardian(s) will be counseled on the avoidance of taking any aspirin or salicylate containing products for 30 days prior to receipt of the first vaccination through 21 days after the last vaccination.
  - All AE/AESIs/NOCMCs/SAEs will be recorded on the appropriate data collection form. AEs will be limited to AESIs and SAEs if after 21 days the first study vaccination. AESIs and NOCMCs will be collected until 3 months and SAEs will be collected throughout the entire study.
  - In the event that the subject attends the visit without a parent/legal guardian, the parent/legal guardian will be called to collect updated medical history, concomitant medications, and will be reminded that the subject is to avoid any aspirin or salicylate containing products for 30 days prior to receipt of the first vaccination through 21 days after the last vaccination.
  - Oral temperature may be obtained if indicated. Subjects must not eat or drink anything hot or cold, or smoke within 10 minutes prior to taking oral temperature.
  - A limited physical examination to specifically include the nares (including edema), throat, and lungs will be done if within 8 days after first vaccination.
  - A targeted physical examination may be performed prior to the second study vaccination, if indicated based on review of interim medical history, by a study clinician licensed to make medical diagnoses and listed on the Form FDA 1572 as the site principal investigator or sub-investigator.
  - A nasal swab for sIgA will be obtained.

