#### **9.4. Type and Duration of Follow-up of Subjects after Adverse Events**

AEs will be collected, assessed, and followed through resolution from the time of each study vaccination through approximately 21 days after the first study vaccination.

AESIs and NOCMCs will be collected, assessed, and followed through resolution from the time of the first study vaccination through approximately 3 months after the first study vaccination. SAEs will be collected, assessed, and followed from the time of the first study vaccination through resolution even if this extends beyond the trial-reporting period (through 12 months after the first vaccination).

Resolution of an AE/SAE is defined as the return to pretreatment status or stabilization of the condition with the expectation that it will remain chronic.

If the site principal investigator or appropriate sub-investigator becomes aware of an acute febrile illness and the site principal investigator or appropriate sub-investigator decides to bring the subject in for an evaluation to determine etiology, then the site principal investigator or appropriate sub-investigator, at their own discretion, can determine if specific viral testing should be done by either culture or polymerase chain reaction (PCR) to determine if the infectious agent was influenza and what strain.

Follow-up procedures, evaluations, and outcomes will be recorded on the appropriate data collection form.

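### Protocol 5.3.4 asks one-dose children to stay for safety follow-up only to about 3 months, which does not fit the 12-month window of the primary SAE outcome

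*Protocol*

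**What the plan says.** Protocol 5.3.4 is the paragraph addressed to children who receive a single dose. It asks them to remain for safety assessments "continuing through approximately 3 months after their first study vaccination", asks for blood at the follow-up visits, and sends the reader to the MOP for alternate follow-up rules. Protocol 6.3, on children who do not get the second vaccination, points back to it: "See Sections 5.3.3 and 5.3.4 for reasons for and handling of withdrawals and discontinuation of treatment".

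The SAE rules carry no condition on dose 2:

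- Protocol 3.2.1 makes SAE frequency a primary outcome, "from receipt of the first vaccination throughout the entire study".
- Protocol 9.1 specifies "SAEs occurring from the time of the first study vaccination through 12 months after the first vaccination". SAP 4.5.2 repeats this.
- Protocol 9.3 states "SAEs will be documented and reported from the time of the first study vaccination through 12 months after the first vaccination", and 9.4 gives the same 12-month reporting period.
- Protocol 7.6 and 7.7, for early termination and unscheduled visits, separate the two windows explicitly: "AESIs and NOCMCs will be collected until 3 months and SAEs will be collected throughout the entire study".
- Protocol 9.3.3 follows a pregnant child, who gets no further dose, for safety to the end of the trial.

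QIV is due at Visit 05 ("Window: 91±14 days post first study vaccination"). After that, V06 is timed 21±2 days, V07 148±14 days and V08 274±14 days after the second vaccination. Protocol Table 2 and Appendix A also print Days 113, 240 and 366 counted from the first vaccination, but without a tolerance.

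**The concern.** Three months is the right end for AESIs and NOCMCs but not for SAEs. It is also about when QIV falls due, so a child becomes a one-dose child at roughly the moment the request to stay expires.

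Dose 1 is the only investigational exposure. A child who then misses QIV has had the full M2SR or placebo exposure, and later SAEs in that child matter as much as in any other. If nobody asks, a new SAE after about Day 92 may not reach the database. Protocol 9.2.3 covers SAEs learned of after follow-up only when they are suspected to be related and the investigator happens to become aware of them. The related-SAE halting rule in 9.5 runs to the child's last study visit, so an earlier last visit shortens that too.

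The analysis would not correct for this. The Safety population in Protocol 11.4.1 includes every child who received at least one dose, SAP Tables 38 and 39 use the Safety Population as N, and SAP 6.5 imputes nothing. SAP Table 12 and Listing 2 would show that follow-up ended early, but an SAE nobody asked about would appear as no SAE.

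**Working it through.** **1. The sections side by side.**

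| Section | Applies to | End of safety follow-up |
|---|---|---|
| Protocol 5.3.4 | one-dose children | about 3 months after dose 1 |
| Protocol 3.2.1 | SAEs, all children | end of study |
| Protocol 7.6, 7.7 | SAEs | end of study |
| Protocol 7.6, 7.7 | AESIs, NOCMCs | 3 months |
| Protocol 9.1, 9.3, 9.4; SAP 4.5.2 | SAEs, all children | 12 months after dose 1 |
| Protocol 9.3.3 | pregnant, no further dose | end of trial |

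Only 5.3.4 attaches a 3-month end to safety follow-up as a whole.

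**2. Days at stake per child.** Day 366 is 365 days after dose 1. I take about 3 months as 91 days, the nominal time of QIV in 7.4.4.

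- 5.3.4 read literally: 365 − 91 = 274 days unsolicited; 274/365 = 75%.
- The child also attends V06 on Day 113 (112 days after dose 1), where SAEs are recorded: 365 − 112 = 253 days; 253/365 = 69%.
- The site follows 9.1 and 9.3 and calls on Days 240 and 366: 0 days.

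**3. Effect on the plan's own detection figure.** Protocol Table 3 gives the chance of at least one event in 25 children as 93% for a 10% risk and 22% for a 1% risk. The formula 1 − (1 − p)^25 gives 92.8% and 22.2%, so the table is reproduced.

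The documents do not give the number of children who miss QIV, so k is an assumption. With k of 25 children observed for 3 of 12 months and a constant hazard, the exponent becomes (25 − k) + k × 3/12:

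| k of 25 (assumed) | Exponent | 10% risk | 1% risk |
|---|---|---|---|
| 0 | 25 | 92.8% | 22.2% |
| 1 | 24.25 | 92.2% | 21.6% |
| 2 | 23.5 | 91.6% | 21.0% |
| 3 | 22.75 | 90.9% | 20.4% |
| 5 | 21.25 | 89.3% | 19.2% |

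**4. Who could be recovered.** Protocol 5.3.3 lists seven reasons for withholding the second dose. Three (withdrawn consent, loss to follow-up, trial termination) are beyond any wording. Two more (investigator decision; new information making participation unsafe) also appear in 5.3.3 as reasons for leaving the trial, so they may or may not leave a child to call. That leaves 7 − 3 − 2 = 2, contraindication to influenza vaccine and refusal of further vaccination, which are specific to dose 2.

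**5. Visit timing without QIV.** With dose 2 on Day 92, 92 + 21 = 113, 92 + 148 = 240 and 92 + 274 = 366, which agree with the printed days. All three stated windows are anchored to dose 2. A child without QIV has target days but no tolerance.

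**The case against.** The strongest reply is that 5.3.4 is a retention request and sets no SAE window. It only encourages children to stay. Every section that defines SAE collection gives 12 months or the whole study. Appendix A marks SAE assessment at V07 and V08 without a dose-2 condition. SAP 6.2 times the final analysis to all enrolled subjects completing Day 366. The next paragraph of 5.3.4 follows events by the collection time for their type, and the MOP may settle the rest.

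Much of this stands. A reader might infer that the protocol stops SAE collection at 3 months in one-dose children. The documents do not support that: the intent elsewhere is clearly 12 months. A reader might also picture some sites asking to 3 months and others to 12. This trial has one site (Protocol Section 5; SAP 6.7), so the question is only which section that site applies.

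The conflict itself remains. The one paragraph written for these children names the earlier end point, and 6.3 sends staff to it. The paragraph on event type concerns events already ongoing at withdrawal, so it does not cover new ones. The MOP is not among the documents, and even a correct MOP would leave the protocol text contradicting itself.

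**Conclusion.** The point holds as an inconsistency in the protocol text that can shorten ascertainment of a primary safety outcome. Its size depends on the reading: up to about 274 of 365 days unsolicited per consenting one-dose child under 5.3.4, and none under 9.1 and 9.3. With one to three of 25 children affected, the detection probabilities in Table 3 fall by about 0.6 to 1.9 percentage points. This rests on 91 days for 3 months, a constant hazard and an assumed number of children. No arm-level total can be given.

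Two further inferences are tempting and should not be drawn. Nothing in the documents suggests that QIV would be missed more often in one arm, so no bias between arms is claimed. Nor are the late calls impossible to schedule without QIV: Days 240 and 366 from dose 1 are printed, and only the tolerance is missing. That part is minor.

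**What to change.** In Protocol 5.3.4, state that, unless consent is withdrawn, SAEs are solicited through 12 months after the first vaccination in every child who received dose 1, whether or not QIV is given, and that AESI and NOCMC collection stays at 3 months.

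As a minor companion change, state in 7.4.5, 7.4.6, 7.5 and Appendix A that if QIV is not given, V06, V07 and V08 are timed from the first vaccination: Day 113, Day 240±14 and Day 366±14.

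The cost is this wording and two phone calls per one-dose child, which every other child already receives. It adds no clinic visit or blood draw beyond those already requested. Protocol 14.8 indicates that enrolment had finished by this version. If follow-up is also complete, the CSR should instead report how far SAEs were solicited in each one-dose child.
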